5.3 Mode of recruitment

Subjects will be recruited by means of posters, flyers, requests on the websites of the participating study groups and institutes, and advertisements in local daily newspapers. During the initial telephone interview, a short interview is conducted to verify that the subjects meet the inclusion criteria of the study. When a sufficiently large number of potential participants has been gathered, "screening" takes place. Study participants will receive an expense allowance of EUR 250.00 at the end of the study.

5.4 Informed consent of study participants

A subject can only be included in the study if he/she has given his/her consent to this after being informed orally and in writing by an investigator about the nature, significance and scope of the study in an appropriate and comprehensible manner.

At the same time as giving his consent, he must have declared that he agrees to the recording of data within the framework of the study and to their review by authorized persons (e.g. monitor, auditor). It must be clear to him that he can withdraw his consent at any time and without giving reasons, without any disadvantages resulting from this.

The original of the written consent will be kept in the study folder of the study center. The subject will be given a copy of the written patient information and the informed consent form. In addition, copies of both documents will be filed in the study folder. Patient information, consent form and all other documents received by the participants as well as recruitment notifications will be submitted to the responsible ethics committee for approval before use. See informed consent forms for both the screening and participation attached at the end of the document.

6. Test medication

6.1 Pharmacological-toxicological expert opinion

Since vitamin A (retinol) can be formed from β -carotene, including in the intestine and liver, it enters the reference values for the desirable daily intake of vitamin A (6 mg β -carotene corresponds to 1 mg retinol). β -Carotene is part of the daily diet and is absorbed mainly with intensely colored vegetables and fruits (spinach, kale, broccoli, lettuce, carrots, tomatoes, pumpkin, mango, etc.). Individuals with a high fruit and vegetable intake (5 servings per day) consume a mean of 36 mg of β -carotene per day (Salter-Venzon et al. 2016). Because β carotene contributes to vitamin A supply but is not itself an essential nutrient, no adverse health effects are expected even with several days of abstinence. In the CARET (Carotene and Retinol Efficacy Trial) study, long-term intake (4 years on average) of 30 mg daily of β -carotene and 25,000 IU retinol (vitamin A) increased the risk of lung cancer in smokers and persons with asbestos exposure, but not in nonsmokers (Omenn et al., 1996). However, no increased risk is expected with a single intake of β -carotene alone. Nevertheless, to exclude any risk, only nonsmokers are included in the study.

The German Nutrition Society (DGE) recommends a daily intake of 10 mg iron for adult men. Adults with normal intestinal function have only a very low risk of being exposed to too much dietary iron (NIH, 2016). However, ingestion of more than 20 mg/kg body weight (equivalent to 1.4 g for an average adult of 70 kg body weight) from dietary supplements or medical

Seite 6 von 11

Version 4 vom 2. Oktober 2017

preparations can cause stomach upset, nausea, constipation, abdominal pain, vomiting, and feelings of weakness, especially if taken fasting. Sustained use of iron supplements containing 25 mg elemental iron or more may result in decreased absorption of zinc and decreased zinc plasma levels. In severe cases (for example, a single dose of 60 mg/kg), iron overdose can lead to multiple organ failure, fainting, coma, convulsions, and even death ((Papanikolaou & Pantopoulos 2005). In the case of a single intake of 25 mg iron (equivalent to the iron content of approx. 100 g blood sausage or pork liver), as planned in the present study, no health risks are to be expected for the subjects.

The daily intake of zinc recommended by the German Nutrition Society (DGE) for adult men is 10 mg. The toxicity threshold for zinc is very high. Acute poisoning with 2 g of zinc causes gastrointestinal disturbances and fever. Acute poisoning from very high doses of zinc manifests primarily as nausea, abdominal cramps, vomiting, tenesmus, and diarrhea (possibly bloody), but is very rare (Maret & Sandstead, 2006). One case study reported severe nausea and vomiting within 30 min of ingesting 4 g of zinc gluconate (equivalent to 570 mg of elemental zinc; NIH, 2016). Daily intakes of 150-450 mg of zinc are associated with low copper status, changes in iron function, lowered immune system activity, and reduced HDL concentrations. Daily intake of 60 mg zinc for 10 weeks resulted in decreased copper-containing enzymes, which are a marker of copper status. The AREDS study with a daily dose of 80 mg zinc in the form of zinc oxide for an average of 6.3 years showed increased hospitalizations for urogenital complaints. This suggests that chronic intake of zinc has effects on certain aspects in urinary tract physiology. Taking 30 mg of zinc once with a commercially available dietary supplement, as planned in the present study, does not pose a risk of adverse health effects to the subjects.

In this study, only commercially available low-dose dietary supplements are used and administered in single doses. Therefore, there are no health risks associated with either the administration of the micronutrients or the one-week washout periods with a low-carotenoid diet for the subjects.

7. medication

7.1 Dosage and mode of administration

Subjects (n=12) will receive, in random order, a single oral dose of 15 mg β -carotene individually plus a placebo capsule (filled with silica and maltodextrin), 15 mg β -carotene plus 25 mg iron (FeSO4), or 15 mg β -carotene plus 30 mg zinc (ZnSO4) in a double-blinded crossover study (interventions separated by one-week washout periods). Commercially available dietary supplements are used for this purpose (β -carotene from BIOVEA, Ferrogamma (iron) and Zinkit® (zinc) from Wörwag Pharma GmbH & Co. KG).

8. study procedure

8.1 Screening

Subjects are considered to be enrolled in the study if they have given their written informed consent to participate in the study (see section 5.4).

First, it is checked that all inclusion criteria are fulfilled and that none of the exclusion criteria are present. For this purpose, a medical history is taken regarding the subjects' health status and dietary and exercise habits. The subjects are weighed and measured. Furthermore, a blood sample will be taken by medical staff (investigator: [name]. [name]). A small blood count will be collected from each subject.

8.2 Hospitalization

The screening of the subjects and the study will take place at the Institute of Biological Chemistry and Nutrition Science. Hospitalization of the subjects is not required.

8.3 Nutrition

Standardized meals will be served on the study days (from the evening before the intervention until the collection of the 10 h blood sample). Subjects will be instructed not to consume foods containing β -carotene (see Subject Information and Supplementary Information) during the studies. An appropriate list of foods and beverages to be avoided will be given to subjects as part of the subject information.

The standardized meals are composed as follows:

Dinner before the first study day consists of farmhouse bread with butter and camembert, plus roasted macadamia nuts and natural yogurt without artificial colors or additives. For breakfast on the study day, fresh wheat rolls with cream cheese (natural) and Greek yogurt are served in parallel with taking the capsules. Lunch on the study day is served four hours after taking the capsules and consists of pasta with cheese sauce, rolls and yogurt ice cream for dessert. The snack 6 hours after intervention consists of ricotta cake. For dinner on the study day, potato salad, farmhouse bread with butter, almonds, and a yogurt are served. All foods used were chosen from the point of view of avoiding additional intake of β -carotene.

8.4 Documentation

Each subject is assigned an ID number and all study data (which preparation the subject received, blood test findings) are recorded under the respective ID number.

8.5 Experimental procedure

Subjects are considered to be enrolled in the study if all inclusion criteria have been met during screening (see section 5.1), none of the exclusion criteria (see section 5.2) are present and the subjects have given their written consent to participate in the study.

On the evening before the intervention, subjects will receive a standardized meal and a standardized snack for consumption between dinner and 10 pm. Subjects will be asked to drink only water and consume no other food after 10 pm and until the intervention on the day of the trial. On the morning of the trial day, subjects will receive a single oral dose of 15 mg β -carotene plus placebo, 15 mg β -carotene combined with 25 mg iron (FeSO4), or 15 mg β -carotene combined with 30 mg zinc (ZnSO4) after breakfast. Standardized meals will be served to study participants throughout the day of the intervention. Blood samples will be collected at baseline (0 h) and 1, 2, 3, 4, 5, 6, 7, 8, 9, and 10 h after ingestion of the study drugs (11 blood samples). A total of approximately 120 mL of blood will be collected per intervention.

As the study is a cross-over study with three arms, after each 1-week washout period, the same experimental procedure is performed in random order with one of the remaining study preparations each time.

8.6 Methods

The blood test (for screening) is performed by the joint practice for laboratory medicine "Laborärzte Sindelfingen" ([name], [contact]).

For the investigation of bioavailability, β -carotene is measured in the blood by means of highpressure liquid chromatography (HPLC), which were taken over the entire period. The appropriate HPLC analysis for this purpose has been established (Stuetz et al 2016). Isolation of the chylomicron fraction is performed according to (Goltz et al 2012).

9. precautionary measures / discontinuation criteria

9.1 Risk-Benefit Consideration.

There is no direct benefit to the subjects of the study. They will receive the result of their blood values, as well as meals on the day of the trial and the evening before. Should indications of health problems of a potential subject come to light in the course of the study or screening, the subject in question will be informed of this by the investigator and, if necessary, advised to consult a specific specialist. The risks of blood collection are a short-term uncomfortable sensation from the needle prick, rarely bruising, and very rarely infection. Participating routine physicians will perform the blood draws so that complications or risks to study participants can be minimized and virtually eliminated.

9.2 Adverse events

Since subjects in the planned study will consume only a single oral dose each of 25 mg iron (FeSO4) and 30 mg zinc (ZnSO4), and only three times a dose of 15 mg β -carotene, no health risks to subjects are expected. As described in 6.1, side effects appeared only with long-term intake of very high doses. Furthermore, in this study only commercially available supplements in the form of capsules are administered.

Nevertheless, the principal investigator agrees to document all UE or Adverse Events (AE) as well as side effects of the supplements or Adverse Drug Reactions (ADR) that might occur during the course of the studies. When AEs or ADRs occur, information on the type, time of occurrence, and duration as well as intensity and frequency of the adverse event will be documented. AE or ADR are defined as events such as mild nausea, mild dizziness, mild reversible change in blood count.

Furthermore, the measure taken as well as a connection with the intake of the preparation or whether the symptom was already known before the start of the study is noted. If the event is related to the study conduct, the investigator commits to immediately exclude the subject from the study.

9.3 Serious Adverse Events and Serious Unexpected Side Effects

Serious adverse events are defined as events that may lead, for example, to hospitalization, persistent disability, life-threatening impairment or even death.

Suspected Unexpected Adverse Reaction (SUSAR) is an adverse event that is inconsistent in nature or severity with the available information on the investigational product, is judged to be serious, and for which a relationship to the investigational drug is judged to be at least possible by the investigator.

9.4 Discontinuation criteria

9.4.1 Discontinuation of the study in one subject (drop-out).

The study is discontinued in an individual subject if the subject withdraws consent to participate in the study, the study protocol is violated, an exclusion criterion or disease occurs, or other circumstances arise that would jeopardize the subject's health if the subject continued to participate in the study.

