4.1 Number of subjects

The required power for the study will be calculated based on the area under the plasma concentration-time curve (AUC). Study power is calculated based on the following formula: n > F (σ /d)2, where n = number of subjects, σ = standard deviation of the dependent primary outcome measure, d = difference between control and treatment classified as significantly different in the literature. The corresponding F-values can be found in the table below; for the planned study, P < 0.05 and 90% power are assumed, resulting in an F-value of 10.51 (Scales & Rubenfeld 2005).

	Power			
Significance level (P-value)	80%	90%	95%	99%
0.100	6,18	8,56	10,82	15,77
0.050	7,85	10,51	12,99	18,37
0.025	9,51	12,41	15,10	20,86
0.010	11,68	14,88	17,81	24,03

F-value Table:

In a comparable study by (Goltz et al. 2013), an AUC of 22.6 \pm 7.6 [nmol*L-1*h] could be determined after intake of 20-30 mg β -carotene (n=6). This results in a mean value of 22.6 nmol*L-1*h and a standard deviation of 7.6 nmol*L-1*h. A reduction of bioavailability by more than one third would represent a biologically relevant effect, which is why a significant difference of rounded up 35%, corresponding to 7.9 nmol*L-1*h, is used for the calculation in this study. Thus, n > 10.51 x (7.6/7.9)2 results in a number of at least 9.7, rounded up to 10 subjects. To allow for a balanced experimental design in which all permutations of the timing of the interventions occur in equal numbers, a total of 12 healthy males aged 18-45 years will be recruited for this study. Females will be excluded from the study because the menstrual cycle affects blood concentrations of carotenoids (Forman et al. 1998).

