5.2 Exclusion criteria

Subjects will not be included in the study should at least one of the following exclusion criteria be present: Use of medication, previous myocardial infarction, addiction, malignant disease, diabetes mellitus, dementia, arterial hypertension, smoking, increased alcohol consumption, use of multivitamin tablets or food supplements, extreme physical stress (>5 hours of exercise

Version 4 vom 2. Oktober 2017

per week) and in case of a known intolerance/hypersensitivity to the preparation (β -carotene, iron, zinc or fillers used).

Subjects enrolled in another study during the same time period or who have participated in another clinical trial within the previous 3 weeks will not be enrolled in the study.

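### Section 9.4.1 stops a man for any protocol violation, however minor, so an early non-health lapse cancels visits that no analysis can recover; the effect is modest and the fix cheap

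*Combined protocol and SAP*

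**What the plan says.** Section 9.4.1 lists alternative grounds for stopping the study in one man: withdrawn consent, then "the study protocol is violated, an exclusion criterion or disease occurs", then other circumstances that would endanger his health if he went on. No ground is graded as minor or major, and investigator discretion is not mentioned. The supplied text has no rule for skipping a visit, replacing a man or handling incomplete sets of visits.

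The procedures to which the violation trigger could apply are these:
- Section 8.5: before each intervention men are asked to drink only water and "consume no other food after 10 pm and until the intervention on the day of the trial".
- Section 8.5: "Blood samples will be collected at baseline (0 h) and 1, 2, 3, 4, 5, 6, 7, 8, 9, and 10 h", that is 11 draws per visit.
- Section 8.3: standardized meals run "from the evening before the intervention until the collection of the 10 h blood sample".
- Section 5.2: the exclusion criteria include "use of multivitamin tablets or food supplements, extreme physical stress" and use of medication, with no dose or duration threshold for supplements or medication.

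Section 4.1 says that the sample size formula "results in a number of at least 9.7, rounded up to 10 subjects". It raises this to 12 so that "all permutations of the timing of the interventions occur in equal numbers". Section 10 names a one-factor repeated-measures analysis of variance.

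**The concern.** All the information on iron and zinc comes from comparing a man with himself. A man stopped at visit 1 gives no comparison, even if his visit 1 AUC is sound. A man stopped at visit 2 gives at most one pair. If the reason was a late snack, those visits were given up without need, and a visit never held cannot be rebuilt by any model.

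The trial has few men to spare. The step from 10 to 12 was made for order balance (12 men over 6 orders, two per order), not as a drop-out allowance. The loss of any one man leaves one order with a single man.

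**Working it through.** **Plan's own figure.** Inputs from section 4.1: F = 10.51 (two-sided 5%, 90% power), SD 7.6, difference 7.9 (35% of 22.6 = 7.91). n > 10.51 × (7.6/7.9)² = 9.73, so 10. This reproduces the plan.

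**Slack in that formula.** Power = Φ(√n × 7.9/7.6 − 1.96):

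| Men | 12 | 11 | 10 | 9 |
|---|---|---|---|---|
| Power | 95.0% | 93.2% | 90.8% | 87.7% |

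Two losses leave power above 90%; three do not.

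**One lapsing man (no SD or lapse rate needed).** Within-man least squares with treatment and period terms, 12 men, two per order, one man reduced, averaged over men. The entries are the rise in variance of the iron or zinc contrast with control.

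| Lapse at | Section 9.4.1 as written | Man continues |
|---|---|---|
| Visit 1 | +10.0%, whether or not that AUC is usable | +5.0% if voided, 0 if usable |
| Visit 2 | +10.0% if voided, +5.0% if usable | +5.0% if voided, 0 if usable |
| Visit 3 | +5.0% if voided, 0 if usable | the same |

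Without the period term, losing a whole man gives 12/11 = 1.091, in place of 1.100. Put into the plan's formula, +10% and +5% correspond to Φ(√(12/1.10) × 7.9/7.6 − 1.96) = 93.0% and Φ(√(12/1.05) × 7.9/7.6 − 1.96) = 94.0%.

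**Average power over a lapse rate p.** The documents give no lapse rate, so p = 2, 5 and 10% of men is assumed, with a lapse equally likely at each visit. Take the 6 orders × 3 lapse visits = 18 cases, with the affected visit voided under both rules and all other collected AUCs used under both:
- As written, only visits before the lapse remain. The control–iron pair is lost in 16 of 18 cases, so q = 8p/9.
- Man continues: the pair is lost only if the lapse hits one of its two visits, 12 of 18 cases, so q = 2p/3.
- Man continues but the next visit is also voided: 16 of 18 again, so q = 8p/9 and the gain is zero.

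Power is that of a two-sided 5% paired t-test (noncentral t, difference 7.9, no period term), averaged over a binomial(12, q) number of lost pairs. The SD of the difference is 7.6 × √(2(1 − r)), where r is the within-man correlation. This equals 7.6 at r = 0.5.

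| p | As written | Man continues | Gain (points) |
|---|---|---|---|
| 2% | 89.8% | 90.0% | 0.2 |
| 5% | 88.7% | 89.2% | 0.5 |
| 10% | 86.6% | 87.7% | 1.1 |

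Over r = 0.3 to 0.7 the gain runs from 0.6 down to 0.2 points at 5%, and from 1.3 down to 0.4 at 10%. If half the affected visits are usable under both rules (q = 13p/18 against p/3), the gain is 0.8 points at 5% and 1.8 at 10%. A pessimistic p = 20% with affected visits voided gives 2.7.

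**The case against.** The case for leaving the clause alone is that it is one sentence in what appears to be a translated text, placed among precautionary measures, and a team would probably read it as meaning a material breach. Stopping violators is also defensible in a small mechanistic study that depends on controlled meals, and it avoids later judgements about which data count. Finally, the gain is small.

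Much of this stands. The material-breach reading is possible, but it is not written. Consent withdrawal is on the same list, so the list is not purely a safety rule. The small gain is accepted.

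A reader might infer more than the text supports:
- *Any unfinished meal or late draw among the 33 (3 × 11) would end participation.* Meals are to be served, and nothing says they must be finished. Sampling times are listed without a window. The 10 pm fast is the only clear rule at the level of the man.
- *One listed food during a washout is a violation.* Section 6.1 speaks only of "the one-week washout periods with a low-carotenoid diet for the subjects", and the subject information cited in section 8.3 was not available.
- *One supplement tablet must stop a man, or should never stop him.* Whether one tablet counts as use under section 5.2 is a matter of interpretation. Because it touches an exclusion criterion, he should not continue automatically.
- *Collected AUCs are thrown away.* Nothing says so.
- *The rule leaves the trial underpowered.* The plan's formula tolerates two losses.

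Comparing the proposal with an analysis of complete men only gives larger gains, but that mixes the stopping rule with the choice of model, so it is not used here.

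**Conclusion.** The point holds as a minor, cheap improvement. Followed literally, section 9.4.1 cancels scheduled visits for a non-health lapse such as a broken fast at visit 1 or 2. The cost for one man stopped at visit 1 is about 10% more variance in each comparison with control, against 0 to 5% if he continues. Averaged over assumed lapse rates of 2 to 10%, the gain is 0.2 to 1.1 points of power with the affected visit voided, and zero if carry-over also voids the next visit. In no case computed does continuing do worse.

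These figures rest on assumed lapse rates, an assumed SD of the difference of 7.6, and the literal reading of the clause. The averages come from paired t-tests and are not the power of the mixed model proposed below. The documents do not show how long a dietary lapse affects later visits. A lapse at visit 3 leaves no later visit to cancel. No bias or safety problem is claimed.

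**What to change.** In section 9.4.1, keep the consent-based and health-based stops, and keep the stop for study-related adverse events in section 9.2. Limit the violation trigger to violations that the investigator judges a health concern. For other minor procedural lapses (fasting, meal, sampling time, diet), record the lapse and let the man attend his remaining scheduled visits. Leave supplement or medication use, which are exclusion criteria, to the investigator's judgement.

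Fix in advance a short list of what makes a visit unusable. Apply it from the lapse record before unblinding and without sight of concentrations, to the affected visit and, where carry-over is plausible, to the next.

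In section 10, replace the repeated-measures analysis of variance with a mixed model with man as random effect and treatment and period as fixed effects. Men with two usable visits then contribute, and unequal orders are adjusted for. This does not by itself restore two men per order, which is kept only where the affected visit proves usable.

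The cost is one paragraph in 9.4.1, one sentence in section 10, one blinded listing, and under section 11 a signed annex reported to the Ethics Committee, possibly with a new vote. Software other than that named in section 10 may be needed. The downside is some blinded usability decisions and some men with only two usable visits. No men, visits or doses are added beyond those scheduled.
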